5.6 Compliance

Individual Product Dispensing and Accountability Logs will be completed for each Participant and kept up to date. The log lists the Participant Number, the date of dispensing, number of capsules dispensed, the number of capsules returned, and the date returned. Participants will be instructed to return all unused product. If applicable, the monitor will inspect the amount of SP dispensed and returned.

Compliance will be assessed at Visit 3, in the statistical analysis, overall compliance will be considered. If a Participant states that they have not returned all unused capsules (e.g., forgot to return, loss, contaminated), details will be recorded in the eCRF. Participants must have consumed a minimum of 80% of the Study Product, in order to be deemed product compliant. Non-compliant Participants will be included in the Intention-to-Treat (ITT) population set (Analyzed on as-randomized basis) and will be excluded withdrawn from the Per-Protocol (PP) analysis.

5.7 Warnings and precautions

- For clinical study use only.
- Keep out of reach of children.

5.8 Concomitant treatments/supplements and restrictions

Participants will be questioned about their general medical history within the previous year, and medications within the previous three months. The details of any medication taken will be recorded in the Participant case notes and case report form.

Participants will be instructed to follow their habitual diet and exercise routine and to not consume any disallowed medications, dietary supplements, probiotic, prebiotic supplements, and fermented products that could interfere with the assessment of the Study Product for the duration of the study.

5.9 Rescue Medication

In case of no bowel movement for more than four days: bisacodyl suppositories or tablets (5- 10 mg) or other rescue medication in line with local guidelines at the dose specified in the local guidelines (no more than three consecutive days over a period of 1 week) will be allowed as rescue medication. Maximum dosage: 15 mg/ day.

Its use needs to be documented at relevant study visits (including concomitant medication, diet, supplements, and any related adverse event). The date and time of rescue medication administration as well as the name and dosage regimen of the rescue medication must be recorded.

The study site will not supply any rescue medication.

6 Study Procedures

Table 2. Schedule of Assessments

Assessment periods						
Visit Number	Visit 1	Run-in	Visit 2	Visit 3	Early Termination Visit	
Visit Window	Day -21 to -15	Day -14 to -1	Day 0	Day 56 + 3 Days		
Study Phase	Screening	Run-in	Intervention			
Screening						
Informed consent	x					
Eligibility Screen	x		x			
Demographic/ Lifestyle data	x					
Medical history	x		x		x	
Anthropometric measurements (Height, weight, BMI)	x					
Prior and concomitant medications	x		x	x	x	
Safety and Tolerability						
Vitals (Blood pressure, heart rate, temperature)	x		x	x	x	
Safety blood parameters	x					

Assessment periods						
Visit Number	Visit 1	Run-in	Visit 2	Visit 3	Early Termination Visit	
Visit Window	Day -21 to -15	Day -14 to -1	Day 0	Day 56 + 3 Days		
Study Phase	Screening	Run-in	Intervention			
(Chemistry profile and Hematology profile)						
AE/SAE			<----->		x	
Assessments/Procedures						
Stool sample collection						
Dispense stool collection kit	x		x			
Return Stool Sample for microbiome analysis			x	x	x	
Urine collection						
Urine pregnancy test	x		x	x	x	
Questionnaires						
Download eDiary App	x					
Bowel Movement & Bristol Stool Scale		x	<----->			
PAC-SYM (Week 0, 4 & 8)			<----->			
PAQ-QoL (Week 0, 4 & 8)			<----->			
Delete eDiary App				x	x	
Dietary analysis						
Dispense 3-Day food Diary	x		x			
Return 3-Day food Diary			x	x	x	
Supplementation						
Randomization			x			
Administer SP			x			
Return SP				x	x	
Assess SP Compliance				x	x	
Participant Compensation						
Dispense Participant Compensation				x	x	

All visits will have the option of being completed remotely via telephone where feasible based on the assessments required for the visit.

6.1 Recruitment procedures

Participants may be recruited through Atlantia's database, social media, radio advertisements and adverts in local newspapers. Participants will undergo an initial pre-screening questionnaire and will be asked questions regarding their age, general health, and medications. Eligible Participants will be scheduled for a Screening Visit.

6.2 Obtaining informed consent

Participants will receive a copy of the Informed Consent Form, via email prior to the Screening Visit. Participants who are foreseen to fulfil the inclusion/exclusion criteria for enrolment into the clinical study will be asked to give informed consent in writing prior to any clinical study specific procedures. Both the Participant (or legal representative) and PI or a person designated by the PI (if acceptable by local regulations) will sign and date the informed consent form. All Participants who have signed the informed consent form will be listed on the *Participant Screening and Enrolment Log* and *Participant Identification Log*.

7 E-Diary/Questionnaire Data Collection

7.1 Daily eDiary Questions

Participants will download an eDiary App at Visit 1 which they will be directed to complete throughout the study. This eDiary will record the following information:

- Bowel movement diary will collect daily data relating to stool frequency and stool consistency.
- AEs and medication use (Weekly)
- Study Product compliance (Weekly)

7.2 eDiary Questionnaires

7.2.1 Patient Assessment of Constipation Symptoms (PAC-SYM) Questionnaire

- Participants will complete the questionnaire at Week 0, Week 4, and Week 8.
- PAC-SYM collects self-reported constipation related symptoms – has a Total Score, and three sub-scores for key symptom areas (Abdominal, Rectal, and Stool related symptoms).

7.2.2 Patient Assessment of Constipation – Quality of Life (PAC-QoL) Questionnaire

- Participants will complete the questionnaire at Week 0, Week 4, and Week 8.
- PAC-QoL assessment collects self-reported impact of constipation on Quality of Life -has a Total Score, and four sub-scores for key areas of wellbeing (Physical Discomfort, Psychosocial Discomfort, Treatment Satisfaction, and Worries & Concerns).

7.3 3-Day Food diary

Participants will complete a 3-Day Food Diary, logging any food eaten for three days prior to Visit 2 to establish their dietary habits at Baseline, and again at Visit 3 to reassess it at end of intervention. This data will be used to confirm that Participants maintained their habitual diet throughout the study via evaluation of key dietary components at baseline compared to end-of-intervention (i.e., energy, total carbs, total sugar, fiber, and fat).

8 Biological measurements and assessments

8.1 Blood sample collection

A total of approximately 7.5mL/0.25 fl.oz of blood should be collected from all Participants.

8.1.1 Failed or partial blood draws

In the case of a failed attempt at a blood draw, or a partial blood draw which did not successfully collect the required amount of blood for analysis, the clinical phlebotomist may either make additional attempts on the Participants other arm, or, if willing, the Participant may be asked to return within the visit window for a second attempt. This will only be carried out if required and will be entirely at the Participant's discretion.

8.1.2 Rejected blood samples or failed blood sample analysis

In the case of a rejected blood sample or failed blood sample analysis, refer to the sub-investigator and the Safety Monitoring Plan.

8.2 Storage of Samples

All blood and fecal samples will be listed on study specific sample logs and stored at the clinical site during the study where applicable.

8.3 Shipment of Samples

Shipment of samples will be performed in accordance with the Laboratory manual.

8.4 Analysis of Samples

All samples will be analyzed using validated assays and methods.

9 Early Participant Withdrawal

Participants have the right to withdraw from the study at any time for any reason, without giving a reason and without penalty or loss of benefits they are entitled to. The PI/Sub-Investigator also has the right to discontinue Participants from SP consumption and/or withdrawal from the study if this is in the best interest of the Participant or if Participant is persistently not compliant with study procedures and SP consumption.

Any of the following conditions may lead to premature withdrawal from SP/study:

- Request by Participant to discontinue for any reason during the study.
- erroneously included / randomized Participant.
- adverse event(s) or concurrent illness that, in the opinion of the PI/Sub-Investigator, warrants the Participant's withdrawal from intervention.
- intake of concomitant medication/dietary supplements prohibited by the protocol.
- Participants who do not follow the requirements of the Protocol, especially those concerning safety and/or if the Participant after their enrolment is uncooperative or not willing to comply with the protocol (non-compliant).

- failure to return for follow-up visits despite numerous attempts to reschedule (lost to follow-up).
- request by regulatory agencies for termination of supplementation of an individual Participant or all Participants under this protocol.
- pregnancy, if a protocol exclusion criterion.

The circumstances of any discontinuation will be in consultation with the Sponsor and must be documented in detail in the corresponding study termination form in the case report form. Whenever a Participant will be withdrawn from the study for whatever reason, adequate efforts will be made to perform a final assessment to include standard medical and laboratory tests which would have been done on normal completion of the study. The data of the withdrawn Participants will be documented in the clinical study report.

Note: Participants who withdraw prematurely from the study will not be replaced.

10 Data processing

10.1 Case Report Form

10.1.1 Electronic Data Capture

It is the responsibility of the PI (or designee) to ensure the completeness and accuracy of the electronic CRFs (eCRF). One eCRF must be compiled for each Participant participating in the study.

Data required for the analysis will be acquired and transferred electronically to a central database by means of an Electronic Data Capture system (the “EDC-tool”). The system operates over the Internet according to the principle of online data capture. Data entered by investigators or data managers into local computers are directly transferred over the Internet to a central database, without any permanent local storage.

High security standards for the transfer and storage study data are guaranteed using technologies such as encrypted data transfer, firewalls, and periodic backup to protect centrally stored data. Writing access to the system will be limited to authorized personnel and the system will automatically keep an audit trail of all entries and corrections to the CRF. Training in the use of the EDC-tool will be provided by data management, study coordinator, monitor, or delegates.

The EDC-tool will comprise of an eCRF, designed specifically for this study.

The EDC-tool is operated under an electronic signature, consisting of the combination of an identification code and a password. In relation to the present study, passwords and electronic signatures will be distributed to users of the EDC tool, and used for entering, modifying, or viewing study data.

It is the responsibility of individuals who received an electronic signature to keep their password secret, i.e., not to reveal it to third parties, and to access the EDC-tool, to enter or modify study data using the EDC-tool only under their personal identification code and password.

10.1.2 Data Management

The eCRF is based on the electronic data capture system developed by Clindox, which is fully compliant with and a Gold Member of the Clinical Data Interchange Standards Consortium.

The eCRF will be hosted on a dedicated validated stand-alone server placed in a double locked server room. All access to the server and other server maintenances will be logged. Study setup and hosting will be managed by Clindox and Atlantia according to ICH-GCP and Standard Operating Procedures.

Only authorized access to the eCRF will be possible using encrypted username and password. Roles in the system are given according to functions (researcher, monitor, project manager, data manager, data analyst etc.). All tasks performed in the eCRF are logged in an audit trail.

The eCRF will contain data ranges and validation checks to maintain an ongoing quality check of data entered. All data validation will be performed as part of the system using Data Clarification Report tools. Ongoing and prior to database lock a blinded database review will be performed, and any discrepancies or missing data will be queried and resolved. A log will be kept on site to document location of source data.

Medical history data, adverse events, and prior and concomitant medication data entry will be standardized.

The PI/Sub-Investigator and authorized staff at the clinical site can add data to the eCRF and must keep the eCRF current to reflect Participant status during the study. A screening and randomization number and the date of birth identify the Participants on the eCRF. The study personnel must make a separate confidential record of personalized details (name and date of birth) on the Participant identification and enrolment log which is kept separately from the eCRF. Once the eCRF for a Participant is completed, the PI/Sub-Investigator will approve the data using an electronic signature and thereby confirm the accuracy of the data recorded.

Laboratory data will be collected electronically from the laboratory and combined with the other clinical data. The data entry of the eCRFs and laboratory data may generate additional requests (Data query) to which the researcher is obliged to respond by confirming or modifying the data questioned.

The eCRFs for any Participant leaving the study should be completed at the time of the final Visit or shortly thereafter. Any ongoing AEs at the final Visit will be characterized as 'Ongoing at End of Study' and there will be no further follow up.

11 Safety and Tolerability

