4.6 Emergency Unblinding procedure

The investigator will receive access to an IWRS to unblind if required.

Unblinding access is for emergency use only, i.e., when it becomes absolutely necessary to know what treatment the participant receives in case of a serious adverse event (SAE) in order to manage the participant's condition. A broken code requires the participant to be withdrawn from the clinical trial.

The investigator should promptly document and notify the Sponsor any premature unblinding (e.g., accidental unblinding, unblinding due to a SAE) of the IP. The date, time, and reason for unblinding must be written onto the envelope and signed by the investigator.

If appropriate, the monitor will check the IWRS during monitoring visits and obtain adequate documentation for any unblinding.

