5.5 Supplementation regimen

5.5.1 Dosage regimen and dose adjustment

- Participants will be provided an eight-week supply of Study Product (5 bags) at Visit 2 in a transparent UniPak, wherein 4 bags will be used for consumption during the eight-week intervention period and 1 bag will be provided as an additional supply in case of delay in study visit or loss of Study Product.
- Participants will be instructed to consume two capsules of the Study Product per day, before breakfast, with a glass of water for the duration of the study (56 days).
- If the dose is missed, the Participant should consume the same dosage after dinner on the same day.
- Missed doses should not be moved to the following day.
- Participants will be instructed to return any unused Study Product at Visit 3.
- Participants will consume their first dose of Study Product on the day following their Visit 2 (Day 1) and will consume their final dose of Study Product on the morning of their Visit 3 (Day 56).

In the event of significant worsening, severe or intolerable new GI symptoms, or other AEs after product consumption/use or overdose, the dose may be interrupted or titrated after consultation with the sponsor representative and PI/Sub-Investigator. The dose may be temporarily interrupted for the shortest time possible without increasing the risk to the Participants continued safety on the study. If the Participant requires dose interruption for more than three days with no improvement in GI symptoms and/or other AEs, then consultation with the Sponsor representative and PI/Sub-Investigator must occur, and the Participant may be discontinued from SP.

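### Section 10.1.2 stops follow-up of every AE ongoing at the final visit, with no exception for SAEs or AEs that caused withdrawal, and Section 11.3 stops investigator follow-up of a pregnancy at the last visit

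*Protocol*

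**What the plan says.** Protocol Section 10.1.2 closes with this rule: "Any ongoing AEs at the final Visit will be characterized as 'Ongoing at End of Study' and there will be no further follow up". The sentence before it concerns the eCRF of any participant leaving the study, so early leavers are included as well as completers.

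Section 4.6 allows emergency unblinding only to manage an SAE, and adds: "A broken code requires the participant to be withdrawn from the clinical trial". For anyone withdrawn, Section 9 says that "adequate efforts will be made to perform a final assessment to include standard medical and laboratory tests". It describes nothing after that assessment. Section 9 also separates stopping the product from leaving the study: the investigator may "discontinue Participants from SP consumption and/or withdrawal from the study".

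Section 11.3 asks for every effort to learn how a pregnancy ended and names live birth, still birth and termination as the outcomes. It asks the participant to report the outcome and presents the investigator's follow-up as the means of helping to secure that report. That follow-up runs, with consent, to the end of the pregnancy or to the last study visit, whichever is earlier.

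**The concern.** Most protocols let minor events lapse at the last visit but keep following serious ones, and those that drove a participant out, until they resolve or stabilise. This protocol states one cut-off for all events. Followed literally, the site need not learn whether a serious event resolved or left sequelae, and the recorded outcome would stay at ongoing. The participants most exposed are those whose event was bad enough to end participation, because withdrawal brings their final visit forward.

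The pregnancy text raises a related problem. The section wants an outcome that, for a pregnancy beginning during the intervention, normally arrives long after the point at which it ends the investigator's follow-up.

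**Working it through.** No figure in the protocol has to be reproduced. The check is a comparison of sections, followed by day arithmetic for pregnancy.

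**1. Does the rule reach SAEs?** Section 11.1 defines an SAE as an AE that meets at least one seriousness criterion. The rule in 10.1.2 applies to any ongoing AE. SAEs are therefore included unless another section exempts them.

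**2. Does another section exempt them or set a longer period?**
- 11.2.3 requires outcomes to be followed and recorded, but only while the study runs. This agrees with 10.1.2.
- 11.4.1 requires an SAE Form and reporting and processing under applicable law. It gives no follow-up period.
- 11.5 sets a 24-hour clock for reporting SAEs to the sponsor. It gives no follow-up period.
- Section 9 gives withdrawn participants one final assessment.
- Table 2 lists no contact after Visit 3 or the Early Termination Visit.
- 8.1.2 mentions a Safety Monitoring Plan, but only for rejected or failed blood samples.

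None of these overrides 10.1.2.

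**3. Who reaches the cut-off with an important event open?**
- A participant unblinded for an SAE, whom 4.6 requires to be withdrawn.
- A participant who leaves the study because of an AE.
- A completer with an SAE still open at Visit 3.

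A participant who stops only the product can stay in the study under Section 9 and is observed until Visit 3.

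**4. How far can a pregnancy have advanced at the last visit?**

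Inputs from Table 2: urine pregnancy tests at Visits 1, 2 and 3; Visit 1 on Day -21 to -15; Visit 2 on Day 0; Visit 3 on Day 56 with a window of +3 days.

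Latest Visit 3 = 56 + 3 = Day 59, and 59 / 7 = 8.4 weeks after the Day 0 test.

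Let u be the days from conception to Day 0 in a pregnancy that the Day 0 test misses. Time from conception at the latest Visit 3 is 59 + u. The protocol gives no value for u; 0 to 14 days is assumed.
- u = 0: 59 days = 8.4 weeks
- u = 14: 59 + 14 = 73 days, and 73 / 7 = 10.4 weeks

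Dating from the last period adds about 14 days (assumed), so the upper value becomes 87 days, and 87 / 7 = 12.4 weeks.

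Still birth is assumed to be possible from about 20 weeks (140 days) on that dating, and live birth only later. Reaching 140 days by Day 59 needs u = 140 - 59 - 14 = 67 days. Such a pregnancy would have been missed at Visit 1, 67 - 21 = 46 to 67 - 15 = 52 days after conception, and missed again at Visit 2 at 67 days. The conclusion does not depend on the exact choice of u.

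A pregnancy first found by the Visit 3 test has 0 days of investigator follow-up under 11.3.

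**5. Which planned results depend on the missing outcomes?** Every safety endpoint in 2.4.2 is an incidence: by causality, severity, MedDRA class and term, laboratory or vital-sign AEs, or SAEs. None uses outcome or duration. An event ongoing at the final visit has already been counted.

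**The case against.** The strongest reply is placement. The sentence sits in a data-management section, directly after a rule on completing the eCRF, and may be meant only as the way to close open AE rows. SAEs have their own form and legal reporting route, and a safety plan that is not shown may say more. This is a plausible account of intent. It does not settle the matter, because the sentence goes beyond coding to end follow-up itself, and no section supplies the follow-up that would then be needed. Even on that reading the exception has to be written.

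A second reply stands in full: this is not a plan to abandon care. Section 11.5 makes a licensed clinician responsible for medical action, and Section 12.2 puts participant safety above the interests of science. What may be lost is the trial's knowledge of the final outcome.

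A reader might infer more than the documents support:

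- **That the trial needs off-product follow-up of all possibly related AEs.** Completers "will consume their final dose of Study Product on the morning of their Visit 3 (Day 56"), so they have no planned off-product days. Table 2 also lists "Delete eDiary App" at Visit 3 and at early termination. These are design choices that contradict nothing in the protocol. With bloating and mild diarrhea the only expected AEs (Section 11.2), calls for every AE rated possible or higher would be a preference.
- **That causality ratings are undermined.** Of the categories in 11.2.1, only Definite uses improvement on stopping, and it can also be met in other ways, such as immediate onset. Under 5.5.1 "the dose may be interrupted or titrated after consultation", so response to stopping can be seen during the study.
- **That 11.3 breaks a promise.** The participant is still asked to report the outcome, which can happen after the last visit, and the list of outcomes can be read as a classification. Likewise, the birth-defect criterion in 11.1, which applies whenever the defect is diagnosed, defines seriousness and sets no surveillance duty. What remains is a tension within 11.3: it relies on investigator follow-up to secure the outcome, then ends that follow-up before a birth can occur.

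**Conclusion.** The point holds as a matter of safety conduct. As written, 10.1.2 ends follow-up of ongoing SAEs and of AEs that caused withdrawal, and no other section in the protocol extends it. Section 11.3 ends investigator follow-up at most 59 days after the Day 0 test, or 8.4 to 10.4 weeks from conception if 0 to 14 undetected days are assumed. For a live birth or still birth it leaves only self-notification.

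The number of affected events cannot be calculated, because the protocol gives no AE, SAE or pregnancy rate. It is probably small: 80 otherwise healthy adults, with contraception required of those who could become pregnant. The efficacy analysis and the incidence of AEs and SAEs recorded by the final visit do not change, and causality ratings are in the main unaffected. A pregnancy complication arising after the last visit, which 11.3 would class as an SAE, would be known only if the participant reported it.

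The protocol should be amended because the edit is cheap and concerns the most serious events, not because any planned result is at risk.

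**What to change.** Three edits:

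- **10.1.2:** except SAEs and AEs that led to withdrawal from the cut-off, and follow them by telephone or record review until resolved or stable. Other AEs can still be closed as ongoing.
- **4.6:** state that withdrawal after unblinding does not end this safety follow-up.
- **11.3:** delete the alternative stopping point at the last study visit, so that follow-up runs to the end of the pregnancy, and keep the condition of the participant's consent.

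The cost is a few contacts per qualifying event, with no added visit for anyone else. Database lock need not wait: SAE or pregnancy outcomes that arrive later can be reported as an addendum to the study report.
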